15.3 REPEATED OR UNSCHEDULED ASSESSMENTS OF SAFETY PARAMETERS

If a participant has repeated assessments before the start of the first treatment, the results from the final non-missing assessment made prior to the start of the DB investigational product will be used as baseline. If end-of-study assessments are repeated or if unscheduled visits occur, the last non-missing postbaseline assessment will be used as the end-of-study assessment for generating summary statistics. However, all postbaseline assessments will be used for PCS value determinations, and all assessments will be presented in the data listings.

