Evaluate SAFER Score Qualification ^g		X					
Modified ATRQ	X						
HAMD-17	X	X				X	
YMRS	X	X				X	
MADRS	X	X	X	X	X	X	
CGI-S	X	X	X	X	X	X	
CGI-I			X	X	X	X	

Study Period	Screening	Baseline	Double-blind Treatment				Safety Follow-up
Visit	1	2	3	4	5	6/ET	7
Study Week	Up to -2^k	0	1	2	4	6^{a,b}	10
Study Day	Up to -14^k	1	8	15	29	43	71
Visit Windows		(within 14 days of start of screening procedures) ^k	± 3 Days	± 3 Days	± 3 Days	± 3 Days	± 3 Days
HAM-A		X		X		X	
SF-12		X				X	
BARS/AIMS/SAS		X	X	X	X	X	
C-SSRS	X	X	X	X	X	X	X
Adverse Events	X	X	X	X	X	X	X
Concomitant Medications	X	X	X	X	X	X	X
Dispense IP		X	X	X	X		
Drug Return and Compliance			X	X	X	X	
ADT Compliance		X	X	X	X	X	
Pharmacogenetic Consent ^h	X			X			
Pharmacogenetic Sample ⁱ				X			
Pharmacokinetic Sample ^j				X	X	X	

Note: After completion of Visit 6/ET, patients will be treated at the discretion of the investigator or designee.

ADT = antidepressant therapy; AIMS = Abnormal Involuntary Movement Scale; ATRQ = Antidepressant Treatment Response Questionnaire; BARS = Barnes Akathisia Rating Scale; CGI-I = Clinical Global Impressions—Improvement; CGI-S = Clinical Global Impressions—Severity; C-SSRS = Columbia—Suicide Severity Rating Scale; ET = early termination; HAM-A = Hamilton Anxiety Rating Scale; HAMD-17 = Hamilton Depression Rating Scale—17 items; IP = investigational product; MADRS = Montgomery-Åsberg Depression Rating Scale; SAS = Simpson-Angus Scale; SF-12 = Short Form-12 v2 Health Survey; YMRS = Young Mania Rating Scale.

^a Performed for all patients, including those prematurely discontinued after randomization (Visit 2).

^b Clinical findings upon termination must be followed until the condition returns to prestudy status or can be explained as unrelated to investigational product. If necessary, an additional follow-up visit should be scheduled.

^c Verified Clinical Trials database check to be performed, where applicable.

^d Clinical laboratory tests include hematology, serum chemistry, urinalysis (including urine myoglobin in patients with creatine phosphokinase levels > 1000 U/L or as clinically indicated for any rise in creatine phosphokinase levels or as necessitated by symptoms), as well as serum pregnancy test in women of childbearing potential.

^e Urine drug screen, blood alcohol concentration (by Breathalyzer), and serum pregnancy test can be repeated at random at request of investigator.

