8.9 Withdrawal Criteria

It is the right and the duty of the Investigator or subinvestigator to stop treatment in any case in which emerging effects are of unacceptable risk to the individual patient. In addition, the Investigator or subinvestigator is to stop treatment of any patient with unmanageable factors that may interfere significantly with the trial procedures and/or the interpretation of results.

A patient must be discontinued from the study for any of the following reasons:

1. The patient misses ≥ 4 consecutive doses of IP and/or ongoing ADT
2. The patient required or initiated hospitalization for his/her psychiatric symptoms
3. The patient decompensates psychiatrically (becomes acutely suicidal, homicidal or psychotic) and in the judgment of the Investigator cannot be safely managed in the study
4. The patient has a positive UDS at any time during the study; for exceptions see Exclusion Criterion 4 and Section [4.5.3](#)
5. The patient experiences 1 of the following elevated liver enzyme conditions, which is confirmed by repeat testing:
 - ALT or AST $> 3 \times$ ULN and total bilirubin $> 2 \times$ ULN
 - ALT or AST $> 8 \times$ ULN
 - ALT or AST $> 5 \times$ ULN for more than 2 weeks

- ALT or AST $> 3 \times$ ULN with the appearance of jaundice, worsening of fatigue, nausea, vomiting, right upper quadrant pain or tenderness, fever, rash, or eosinophilia

6. The patient has an absolute neutrophil count (ANC) of < 1000 per mm³ and, after repeat testing within 24 hours of awareness, the values are not normalized or are not increasing
7. A female patient becomes pregnant during treatment

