10.2 CLINICAL LABORATORY PARAMETERS

Descriptive statistics for clinical laboratory values (in SI units) and changes from the baseline values at each assessment time point will be presented by treatment group for the following laboratory parameters:

Hematology:	Absolute and differential white blood cell count, erythrocyte count, hemoglobin, hematocrit, platelet count, and red blood cell indices (mean corpuscular volume, mean corpuscular hemoglobin, and mean corpuscular hemoglobin concentration)
Chemistry:	Sodium, potassium, calcium, chloride, bicarbonate, glucose, blood urea nitrogen, creatinine, total protein, alkaline phosphatase, albumin, total bilirubin, direct bilirubin, indirect bilirubin, AST, ALT, free T3, free T4, TSH, lactate dehydrogenase, creatine phosphokinase, γ -glutamyl transpeptidase, uric acid, phosphate, lipid panel (total cholesterol, triglycerides, low-density lipoproteins, high-density lipoproteins), prolactin, insulin, and magnesium
Urinalysis:	Specific gravity, pH

In addition, descriptive statistics for values and changes from the baseline values in conventional units at each assessment time point will be presented for selected clinical laboratory parameters listed in [Appendix II](#). A description of reporting the lab values in conventional units in participant narratives (along with the standard reporting in SI units) is presented at the end of [Appendix II](#). Only participants with clinical laboratory data at baseline and at least one postbaseline visit during the double-blind period will be included in the summary.

Laboratory tests values are considered to be potentially clinically significant (PCS) if they meet either the low or high PCS criteria listed in [Table 10-1](#). The number and percentage of participants with PCS postbaseline clinical laboratory values will be tabulated by treatment group. The percentages will be calculated relative to the number of participants with available non-PCS baseline values and at least 1 postbaseline assessment. The numerator will be the total number of participants with available non-PCS baseline values and at least 1 PCS postbaseline value. A supportive listing of participants with PCS postbaseline values will be provided, including the participant identification number, study center number, and baseline and postbaseline values. A listing of all AEs occurring in participants who have PCS laboratory values will also be provided.

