10.4 ELECTROCARDIOGRAM

Descriptive statistics for ECG parameters (heart rate, RR interval, PR interval, QRS interval, QT interval, QTcB interval, and QTcF interval) and changes from baseline values at each assessment time point to the end of the DB treatment period will be presented by treatment group. The QTc will be calculated using both the Bazett and Fridericia corrections (if the vendor does not provide).

Electrocardiographic parameter values are considered PCS if they meet or exceed the higher-limit PCS criteria listed in Table 10-4. The number and percentage of participants with PCS postbaseline ECG values will be tabulated by treatment group for the double-blind treatment period. The percentages will be calculated relative to the number of participants with available non-PCS baseline values and at least 1 postbaseline assessment for the double-blind treatment period. The numerator is the total number of participants with available non-PCS baseline values and at least 1 PCS postbaseline value for the double-blind treatment period. A supportive tabular display of participants with PCS postbaseline values will be provided, including the participant identification (PID) number, baseline, all postbaseline (including non-PCS) values, and change from baseline.

In addition, a tabular display showing all AEs that occurred in participants who had postbaseline PCS ECG values will be provided.

A shift table from baseline to the end of study in the Investigator's overall interpretation of the ECG will be presented by treatment group for the following categories: normal; abnormal, not clinically significant; abnormal, clinically significant. A tabular display showing participants with postbaseline clinically significant ECG abnormalities according to the Investigator's overall interpretation will be provided.

Table 10-4 Criteria for Potentially Clinically Significant Electrocardiograms

Parameter	Unit	Higher Limit
QRS interval	msec	≥ 150
PR interval	msec	≥ 250
QTc (QTcB or QTcF) interval	msec	>500
QTc (QTcB or QTcF) interval	msec	Increase of > 60

QTc = QT interval corrected for heart rate.

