15.0 DATA HANDLING CONVENTIONS

15.1 VISIT TIME WINDOWS

Table 15-1 presents the visits assigned for efficacy and safety analyses and the corresponding range of treatment days (window) during which an actual visit may occur.

Table 15-1 Efficacy and Safety Analysis Visit Definitions

Analysis Phase	Derived Visit	Scheduled Visit Day ^a	Window
Pretreatment	Baseline	Day 1	Days ≤ 1
Double-blind Treatment	Week 1	Day 8	Days [2, 11]
	Week 2	Day 15	Days [12, 21]
	Week 4	Day 29	Days [22, 35]
	Week 6	Day 43	Days ≥ 36 and within Double-blind Treatment Period
	End of Double-Blind Treatment Period ^b	Final double-blind treatment visit (expected Day 43) or ET visit during the double-blind treatment period	Final non-missing assessment during the double-blind treatment period
Safety Follow-up	Week 10	Day 71	day of final double-blind or ET visit during the double-blind treatment period $+1 \leq \text{Days} \leq \text{last visit}$

a Relative to the date of the first dose of double-blind investigational product. Day 1 = the date of the first dose of double-blind investigational product.

b Presented in analysis tables for safety parameters, including but not limited to electrocardiograms, clinical laboratory values, and vital signs.

ET = early termination.

If the visit date is on or after the date of the first dose of double-blind investigational product, the study day is calculated by visit date – date of the first dose of double-blind investigational product + 1. If the visit date is before the date of the first dose of double-blind investigational product, the study day is calculated by visit date – date of the first dose of double-blind investigational product. Therefore, a negative day indicates a day before the start of the double-blind investigational product.

If a participant has 2 or more visits within the same window, the last visit with a non-missing value will be used for analysis.

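### SAP 15.3 sets no time limit on the end-of-study safety value, so ECGs taken after dosing has stopped can enter the investigator ECG-interpretation shift table

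*SAP*

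**What the plan says.** SAP 15.3 covers repeated and unscheduled safety assessments. When an end-of-study assessment is repeated, or an unscheduled visit occurs, "the last non-missing postbaseline assessment will be used as the end-of-study assessment for generating summary statistics". The next sentence limits the reach of that rule: "However, all postbaseline assessments will be used for PCS value determinations, and all assessments will be presented in the data listings".

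SAP Table 15-1 defines a different quantity, the End of Double-Blind Treatment Period value, as the "Final non-missing assessment during the double-blind treatment period". Its footnote b says this row is presented in the safety tables, including ECG, laboratory and vital signs. SAP 10.0 closes the double-blind period at the last scheduled Visit 6/ET assessment and starts safety follow-up the next day.

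SAP 10.4 uses both labels. Descriptive ECG statistics stop at the end of double-blind treatment, and PCS counts are for that period. The investigator's overall interpretation is instead summarised as "A shift table from baseline to the end of study".

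Protocol Table 1 schedules ECG at Visit 1 and Visit 6/ET only. Footnote b to that table states: "Clinical findings upon termination must be followed until the condition returns to prestudy status or can be explained as unrelated to investigational product". It continues: "If necessary, an additional follow-up visit should be scheduled". Protocol 12.2.4.3 allows the ECG to be left out of a remote visit and asks for it to be done unscheduled during safety follow-up.

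**The concern.** For ECG, the assessment that 15.3 calls end-of-study has one scheduled source, Visit 6/ET. Any later ECG is taken after dosing has stopped, because no investigational product is given in follow-up (Protocol 5.5). Nothing in the documents calls for a normal Visit 6 ECG to be repeated, whereas an abnormal finding must be followed. If the later reading replaces the Visit 6 reading, replacement depends on the result and tends towards recovery.

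At stake is a by-arm safety table. The ECG PCS criteria in SAP Table 10-4 cover only QRS, PR and QTc. For any other abnormality that the investigator judges clinically significant, the shift table is the only by-arm count the SAP specifies.

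**Working it through.** The plan states no figure on this point to reproduce. The check sets the rules side by side, traces two participants, and then gives an illustration with assumed rates.

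**1. Which rule governs which output**

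| Output | Time limit in the SAP | Can a follow-up value replace Visit 6/ET? |
|---|---|---|
| Quantitative ECG (10.4) | To end of double-blind treatment | No |
| Vital signs (10.3) | Each visit and end of double-blind treatment | No |
| Laboratory values (10.2) | Each assessment time point; Table 15-1 end-of-double-blind row | Not under Table 15-1 |
| PCS counts (15.3, 10.2–10.4) | Every postbaseline value used (10.4: double-blind period) | No: a later normal value does not cancel an earlier PCS value |
| Listings (15.3) | All assessments | No |
| Investigator ECG shift (10.4) | End of study | Yes, under 15.3 |

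For laboratory data, 10.2 adds: "Only participants with clinical laboratory data at baseline and at least one postbaseline visit during the double-blind period will be included in the summary". That restricts who is summarised, not which value is used. The protection against a later value therefore comes from Table 15-1, and 15.3 read alone contradicts it.

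Nothing in the SAP equates end of study with end of double-blind treatment. Protocol 9.4 attaches the abbreviation EOS to Visit 7, the follow-up visit, so a programmer could reasonably let the shift table run past Visit 6.

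**2. Two participants**

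- *Follow-up of an abnormality.* The Visit 6 ECG is read as abnormal and clinically significant. An extra ECG in follow-up is read as normal. Under 15.3 the shift table shows normal; under Table 15-1 it shows abnormal, clinically significant.
- *COVID-19 catch-up.* Visit 6 is remote and the ECG is omitted. It is done unscheduled in follow-up, or later still if the participant cannot return in that period (Protocol 12.2.5). Under 15.3 it is the end-of-study value. Under Table 15-1 the participant has no end-of-double-blind ECG. Here no on-treatment reading is lost, but a post-dosing reading is counted with on-treatment ones.

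**3. Illustration (assumed rates; the documents give none)**

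Let p be the share of an arm with a clinically significant abnormal reading at Visit 6/ET, and r the share of those replaced by a normal follow-up reading. The shift table then shows p × (1 − r).

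| p, cariprazine vs placebo | r = 0 | r = 25% | r = 50% | r = 100% |
|---|---|---|---|---|
| 2% vs 1% | 2% vs 1% | 1.5% vs 0.75% | 1% vs 0.5% | 0% vs 0% |
| 5% vs 2% | 5% vs 2% | 3.75% vs 1.5% | 2.5% vs 1% | 0% vs 0% |
| 10% vs 4% | 10% vs 4% | 7.5% vs 3% | 5% vs 2% | 0% vs 0% |

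In the middle row the absolute difference falls from 3 points (5 − 2) to 2.25 (3.75 − 1.5), then 1.5 (2.5 − 1), then 0. With the same r in both arms, the ratio of the arms is unchanged (5/2 = 3.75/1.5 = 2.5) until r reaches 100%. What is lost is the absolute level and difference.

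**The case against.** The strongest reply is that the SAP already has the right rule. Table 15-1, its footnote b and SAP 10.0 together assign anything after the last scheduled Visit 6/ET assessment to safety follow-up. On that view, end of study in 10.4 is loose wording for end of double-blind treatment. SAP 10.4 also requires a display of every participant with a postbaseline clinically significant ECG abnormality, so no case would be hidden. And Protocol Table 1 footnote b does not order each abnormal ECG to be repeated until normal: follow-up also ends when a finding is explained as unrelated, and an extra visit is only as needed.

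Much of this stands, and it confines the point to one table. It does not remove it. 15.3 has no time limit or cross-reference, 10.4 uses two labels within one section, and the display is by participant rather than a count by arm.

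A reader might infer three stronger things that the documents do not support.

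- *That mean changes in laboratory values, vital signs or ECG intervals are biased.* If 15.3 alone governed, the loss in a mean difference would be (pC − pP) × r × e, where e is the size of the excursion in SD. For the rates above and e of 2 to 3, that runs from 0.01 × 0.25 × 2 = 0.005 SD to 0.06 × 1 × 3 = 0.18 SD. Under Table 15-1 the loss from a follow-up repeat is zero.
- *That abnormalities are overwritten throughout the safety analysis.* PCS determinations use every postbaseline value and listings show all of them. Worst-value summaries are planned for lipids and glucose (10.2) and hypertension status (10.3).
- *That the comparison is tilted in favour of cariprazine.* The rule applies to all arms. A between-arm effect needs more abnormalities on drug and recovery in follow-up. Neither is documented, and the sponsor extended follow-up to 4 weeks because of the drug's long half-life (Protocol 12.4), so exposure does not end with the last dose.

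The COVID-19 route is also narrow for laboratory data, since results from alternate laboratories stay in source and are not entered in the eCRF (Protocol 12.2.4.2).

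**Conclusion.** The point holds for the investigator ECG-interpretation shift table. As written, that table can take an ECG from after the end of dosing, and where the ECG was done to follow up an abnormality this can understate what was present on treatment. For laboratory, vital-sign and quantitative ECG summaries, 15.3 conflicts with Table 15-1 on paper, but the more specific provisions largely protect them.

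The size cannot be derived from the documents: they give no abnormality, repeat or recovery rates. The percentages above rest on assumed values and on complete recovery of the replaced readings. That 15.3 governs the shift table is an inference from the shared end-of-study label. Efficacy results, PCS counts, adverse events and listings do not change. This is a modest correction to a descriptive table, worth making because it affects what that table reports by arm and costs very little.

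**What to change.** - **SAP 15.3:** state that end-of-treatment summary statistics use the last non-missing assessment inside the double-blind period of Table 15-1. Later repeats and COVID-19 catch-up tests are used only for PCS determinations, listings and follow-up-period summaries.
- **SAP 10.4:** define the interpretation shift table as baseline to end of the double-blind treatment period. Add a second shift from baseline to the worst postbaseline interpretation in that period, which also captures unscheduled on-treatment ECGs.
- **Follow-up ECGs:** show participants whose only postbaseline ECG was done in follow-up separately from the main shift table.

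No rule choosing the first of several repeated values is needed; the double-blind limit is enough, and it keeps the SAP's last-value convention.

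The cost is a few sentences and one change to the safety analysis flags, with no change to visits or procedures. The small downside is that participants with only a follow-up ECG leave the main shift table, so its denominator falls by that number.

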15.4 MISSING DATE OF THE LAST DOSE OF STUDY TREATMENT

When the date of the last dose of study treatment is missing for a participant in the Safety Population, all efforts should be made to obtain the date from the Investigator. If after all efforts are made it is still missing, the last available dosing record date will be used as the last dose date.

15.5 MISSING SEVERITY ASSESSMENT FOR ADVERSE EVENTS

If severity is missing for an AE that started before the date of the first dose of study treatment, an intensity of mild will be assigned. If severity is missing for an AE that started on or after the date of the first dose of study treatment, an intensity of severe will be assigned. The imputed values for severity assessment will be used for the incidence summary; the values will be shown as missing in the data listings.

15.6 MISSING CAUSAL RELATIONSHIP TO STUDY DRUG FOR ADVERSE EVENTS

If the causal relationship to the study treatment is missing for an AE that started on or after the date of the first dose of study treatment, a causality of yes will be assigned. The imputed values for causal relationship to study treatment will be used for the incidence summary; the values will be shown as missing in the data listings.

15.7 MISSING DATE INFORMATION FOR ADVERSE EVENTS

The following imputation rules only apply to cases in which the start date for AEs is incomplete (ie, partly missing).

Missing month and day

- If the year of the incomplete start date is the same as the year of the first dose of study treatment, the month and day of the first dose of study treatment will be assigned to the missing fields
- If the year of the incomplete start date is before the year of the first dose of study treatment, *December 31* will be assigned to the missing fields
- If the year of the incomplete start date is after the year of the first dose of study treatment, *January 1* will be assigned to the missing fields

Missing month only

- If only the month is missing, the day will be treated as missing and both the month and the day will be replaced according to the above procedure

Missing day only

- If the month and year of the incomplete start date are the same as the month and year of the first dose of study treatment, the day of the first dose of study treatment will be assigned to the missing day
- If either the year of the incomplete start date is before the year of the date of the first dose of study treatment or if both years are the same but the month of the incomplete start date is before the month of the date of the first dose of study treatment, the last day of the month will be assigned to the missing day
- If either the year of the incomplete start date is after the year of the date of the first dose of study treatment or if both years are the same but the month of the incomplete start date is after the month of the date of the first dose of study treatment, the first day of the month will be assigned to the missing day

If the stop date is complete and the imputed start date as above is after the stop date, the start date will be imputed by the stop date.

If the start date is completely missing and the stop date is complete, the following algorithm will be used to impute the start date:

- If the stop date is after the date of the first dose of study treatment, the date of the first dose of study treatment will be assigned to the missing start date
- If the stop date is before the date of the first dose of study treatment, the stop date will be assigned to the missing start date

